A Prospective, Randomized Controlled Study Comparing the Integrated Posterior–Anterior– Lateral (PAL) Approach and the Posterior Approach in Robot-Assisted Radical Prostatectomy

Research Protocol

Research Unit: The First Affiliated Hospital of Zhengzhou University

Principal Investigator: [name]

Contact Number: [name]

NCT ID: Not yet assigned

May 15, 2024

I. Research Background

Radical prostatectomy is the standard treatment for localized prostate cancer. Rassweiler et al. first reported robot-assisted radical prostatectomy (RARP) in 2001. Given the Da Vinci robot's high-definition three-dimensional imaging technology and flexible yet stable robotic arms, it is particularly suited for performing more precise dissection, anatomy, and suturing within confined spaces. Consequently, RARP has rapidly gained popularity worldwide and has even replaced traditional laparoscopic and open surgery in some hospitals. Patel et al. proposed the "pentafecta" for radical prostatectomy: long-term cancer control, urinary continence preservation, erectile function preservation, absence of surgical complications, and negative surgical margins. This remains the goal pursued by urologists. To achieve better treatment outcomes for patients, surgeons domestically and internationally have conducted in-depth research on various RARP approaches, such as the anterior approach, posterior approach lateral approach, and transvesical approach. However, each RARP approach has its own advantages and disadvantages. To maximize the benefits of each approach, based on our center's experience with over 1000 radical prostatectomies, we were the first in China to propose the PAL combined approach RARP in 2022. This approach involves initially using the posterior approach to separate the vas deferens, seminal vesicles, and Denonvilliers' fascia, followed by the anterior

approach to separate the retropubic space, and then the lateral approach to separate the bladder neck and preserve the neurovascular bundles (NVB) as much as possible.

II. Study Objectives

(1) Study Objective

This study aims to compare the perioperative outcomes, pathological results, and early functional outcomes of the PAL combined approach RARP and the posterior approach (Retzius-sparing) RARP in the treatment of prostate cancer.

(2) Study Significance

1. To provide a new, safe, and effective surgical approach (not a non-surgical method) for robotic radical prostatectomy in clinical practice.
2. To provide a better foundation for the application of the PAL combined approach RARP.

III. Research Trial Management

The center will appoint one Principal Investigator overall, one Co-Investigator, and one Lead Statistician. Standardized statistical analysis methods will be applied. The trial will be conducted strictly in accordance with the protocol, ensuring the timely, accurate, and truthful completion

of case report forms. Researchers will receive training prior to the trial's initiation to familiarize themselves with the study protocol and unify assessment criteria.

Laboratory test reports must contain all essential items, including the date, test items, test results, and their normal reference ranges. A strict serious adverse event reporting system will be established.

If you have any questions regarding this study, you may contact the Principal Investigator.

Name	Role in Study	Phone Number
[name]	Principal Investigator	[name]
[name]	Investigator	[name]
[name]	Investigator	-
[name]	Investigator	-
[name]	Investigator	-

IV. Rationale for the Trial

1. Surgeons domestically and internationally have conducted in-depth research on various RARP approaches, such as the anterior, posterior, lateral, and transvesical approaches. However, each RARP approach has its own advantages and disadvantages.
2. Our center was the first in China to propose the PAL combined approach RARP in 2022. This approach involves initially using the posterior approach to separate the vas deferens, seminal vesicles, and Denonvilliers' fascia, followed by the anterior approach to separate the retropubic space, and then the lateral approach to separate the bladder neck and preserve the neurovascular bundles (NVB) as much as

possible. There are currently no prospective studies comparing this combined approach with other approaches.

V. Subject Selection and Withdrawal

(1) Inclusion Criteria:

Age \geq 40 years and \leq 80 years;

Patients diagnosed with prostate cancer by prostate biopsy;

Clinical T stage \leq T3a;

Full understanding of the clinical trial protocol and provision of signed informed consent.

Any outpatient or inpatient volunteer patient who meets all the above criteria can be enrolled as a subject.

(2) Exclusion Criteria:

Pre-existing urinary incontinence;

Previous endoscopic prostate surgery;

Presence of severe underlying diseases rendering the patient unable to tolerate surgery or with a life expectancy of < 5 years;

Presence of metastatic disease or suspected lymph node involvement at diagnosis;

Patients deemed by the investigator as unsuitable for participation in this clinical trial.

Any patient meeting any of the above criteria cannot be enrolled as a subject.

(3) Discontinuation (Withdrawal) Criteria:

This refers to all patients who have signed the informed consent form, passed screening, and entered the trial but subsequently withdraw from the clinical trial.

Common reason: The patient requests to stop the trial.

When a patient discontinues, the investigator must record the reason for discontinuation in the case report form and complete all possible assessments and examinations, documenting the last condition, including the last trial-related procedures performed. For discontinuations due to adverse events, this must be recorded in the case report form, and the sponsor must be notified. Discontinued cases will be included in the analysis according to different scenarios.

VI. Study Protocol

Study Design

This is a prospective, randomized controlled, single-center clinical study. It primarily aims to compare the perioperative outcomes, pathological results, and early functional outcomes of PAL combined approach RARP and posterior approach (Retzius-sparing) RARP in the treatment of prostate cancer. All patients meeting the inclusion/exclusion criteria will be randomly assigned to one of two groups: the PAL combined approach group or the posterior approach group. This study plans to enroll no fewer than 30 patients per group.

Inclusion Criteria

Detailed inclusion and exclusion criteria are listed above. The key inclusion criterion is patients diagnosed with prostate cancer by biopsy and scheduled to undergo robot-assisted radical prostatectomy.

Randomization

Eligible subjects will be randomized in a 1:1 ratio to either the PAL combined approach group or the posterior approach group. The randomization process will be performed by an independent, dedicated statistician.

Surgical Methods

All patients will undergo surgery according to the standard procedures for robot-assisted radical prostatectomy.

Posterior Approach (Retzius-sparing) RARP: Adhesions of the sigmoid colon are first released to expose the pouch of Douglas. The peritoneum is incised at the rectovesical pouch, taking care not to damage the ureters. The bilateral vas deferens are carefully dissected. Following the bilateral vas deferens leads to the identification and dissection of the bilateral seminal vesicles. The small arteries of the seminal vesicles can be managed using Hem-O-lok clips before cold knife transection, or using bipolar coagulation before transection. The bilateral seminal vesicles are freed. Denonvilliers' fascia is incised, and blunt dissection is performed along the anterior rectal fat plane towards the prostate apex. The parietal peritoneum of the rectovesical reflection is incised. The seminal vesicles and vas deferens are dissected and transected. Denonvilliers' fascia is incised transversely. Blunt dissection is performed along the posterior plane of the prostate towards the apex. The bladder neck is dissected and incised. Blunt dissection is performed intrafascially towards the apex. The puboprostatic ligaments and posterior urethra are dissected and transected, and the prostate is completely removed.

PAL Combined Approach RARP: Posterior Access The sigmoid colon was mobilized, and dissection proceeded along the posterior bladder wall to expose the pouch of Douglas. The rectovesical peritoneal reflection was incised to identify and preserve the bilateral ureters, vas deferens, and seminal vesicles. Dissection was performed dorsal to the seminal vesicles to identify and open Denonvilliers' fascia. The fascia was then dissected along the posterior plane of the prostate until reaching the prostatic apex, with careful attention to avoiding rectal injury. The vas deferens was subsequently transected, and the seminal vesicles were dissected. A triangular anatomical zone was developed

between the bladder neck, prostate base, and right neurovascular bundle to facilitate subsequent dissection steps. **Anterior Access** The preperitoneal space was developed by dividing the medial umbilical ligaments and the urachus, gaining access to the retropubic space (Fig. 1D). At this stage, the dorsal vascular complex was left intact. The endopelvic fascia, puboprostatic ligaments, and other anterior supporting structures were preserved to maintain anatomical integrity. **Lateral Access** The dissection plane along the bladder neck was defined. Building on the previously developed posterior plane, the triangular space bordered by the bladder, prostate base, and neurovascular bundle was further expanded. The mobilized seminal vesicles were retracted through this corridor to provide controlled traction. The bladder neck was then sharply divided close to the prostate, releasing any residual attachments and preserving surrounding muscle and connective tissue. The prostatic pedicles were subsequently clipped and dissected under direct vision to maintain hemostasis and anatomical precision. **Neurovascular Bundle Dissection** With the right seminal vesicle retracted toward the midline, a working plane was developed between the prostatic capsule and surrounding fascia. Dissection proceeded in an antegrade manner to release the neurovascular bundle without the use of thermal energy. The same approach was applied to the contralateral side to ensure bilateral nerve preservation. **Apical Dissection and Urethral Division** The prostate was elevated cephalad to expose the apex and adjacent posterior structures. Dissection at the apical region was performed with careful attention to preserving the maximal length of the urethral stump. Blunt and sharp dissection was carried out beneath the dorsal venous complex to avoid injury to anterior vascular structures. The pelvic fascia and puboprostatic ligaments were preserved. The urethra was then incised posteriorly under direct vision, completing the apical dissection and

allowing for en bloc removal of the prostate. After prostate dissection, continuous urethrovesical anastomosis was performed using a 3-0 suture.

VII. Observation Indicators

Primary Observation Indicator:

The primary observation indicator is the urinary continence rate after catheter removal. The urinary continence rate is defined as the number of patients with recovered continence per group divided by the total number of patients in that group. Urinary continence rates will be assessed at 1 day, 1 week, 3 months, 6 months, and 1 year after catheter removal. Recovery of urinary continence is defined as not using any pads or using only 1 safety pad per day with no leakage. Urinary incontinence is defined as using more than 1 pad per day. Immediate continence and early continence are defined as recovery of continence within 7 days and within 3 months after catheter removal, respectively.

Secondary Observation Indicators:

- (1) Perioperative indicators, such as: operative time, estimated blood loss, intraoperative and postoperative complications, time to drain removal, postoperative hospital stay;
- (2) Positive surgical margin status in the pathology report.

VIII. Ethical Requirements and Patient Informed Consent

This clinical trial will be conducted in accordance with the Declaration of

Helsinki (1996 version) and relevant Chinese regulations and guidelines for clinical trial research. The trial protocol must be approved by the Ethics Committee of each participating institution before the trial commences.

Before each patient is enrolled in this trial, the investigating physician is responsible for providing a complete and comprehensive explanation, in written form, to the patient or their designated representative, regarding the trial's purpose, procedures, and potential risks. Patients should be informed that they have the right to withdraw from the trial at any time. Each patient must be given a copy of the informed consent form before enrollment. The investigating physician is responsible for ensuring that each patient signs the informed consent form before entering the trial and for retaining the form in the study files.

IX. Statistical Analysis

Statistical tests will employ parametric methods or models wherever possible. All statistical tests for indicators will be two-sided, and a P-value ≤ 0.05 will be considered statistically significant.

Descriptive statistics for quantitative indicators will include the mean, standard deviation, median, and interquartile range. Descriptive statistics for categorical indicators will include counts and percentages. Statistical analysis will be performed using professional software such as SPSS, SAS, and R.

X. Data Retention

The investigator shall retain all study documents, including identification of all participating subjects (enabling effective cross-referencing of different records, such as hospital source records), all original signed informed consent forms, and all case report forms, etc. The investigator shall retain the clinical trial data for 5 years after the completion of the clinical trial.

XI. Expected Timeline for the Clinical Trial

- (1) Trial preparation period: Month 1.
- (2) Clinical trial observation period: Months 2 – 8.
- (3) Data collection, statistical analysis, and summarization period: Months 8 -18.

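### Does the Section V sentence on discontinued cases let randomised patients drop out of the primary continence rate?

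*Protocol*

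**What the plan says.** Section V(3) defines discontinued cases as patients "who have signed the informed consent form, passed screening, and entered the trial but subsequently withdraw from the clinical trial". It names one common reason, the patient's own request, and also foresees stopping because of an adverse event. The investigator must record the reason and "complete all possible assessments and examinations, documenting the last condition". The section ends: "Discontinued cases will be included in the analysis according to different scenarios".

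Section VI (Study Design) states: "All patients meeting the inclusion/exclusion criteria will be randomly assigned to one of two groups". It also gives the only sample-size figure: "This study plans to enroll no fewer than 30 patients per group".

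Section VII defines the primary measure, the continence rate, as "the number of patients with recovered continence per group divided by the total number of patients in that group". It is assessed at five times, from one day to one year after the catheter comes out, and no exception is made for discontinued cases.

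Section IX sets two-sided tests at 0.05. It names neither a test for the continence rate nor an analysis population.

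**The concern.** Read together, Sections V and VI put the sentence on discontinued cases after randomisation, so it is not about screening failures. If inclusion depends on criteria that are not written down, someone could decide late which men count, with the reason for stopping and the last recorded condition already on the case report form. That would sit badly with the full-group denominator in Section VII.

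The stake would be the randomised comparison itself. If men left the analysis for reasons tied to the operation or to leakage, the groups compared would no longer be those formed by random assignment. At 30 per arm each man is worth 1/30 = 3.3 percentage points, so a few removals can matter near the 0.05 line.

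**Working it through.** **1. The texts side by side.** There are two ways to read the Section V sentence.

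- *All discontinued men are included, and their handling differs by scenario* (for example, withdrawal before surgery, before catheter removal or during follow-up). This agrees with the Section VII denominator.
- *Only some are included.* This would clash with Section VII if its group total means all assigned men. But the sentence does not say so, and no other section excludes anyone.

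Section VII does not use the word randomised. Since the groups are formed by assignment, however, the natural reading is everyone assigned. On that reading the specific endpoint definition already fixes the denominator, and the general sentence in Section V does not displace it. If the group total meant something narrower, there would be no conflict between the sections. The clash needs the exclusion reading of Section V together with the all-assigned reading of Section VII.

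**2. How much an exclusion could move the result.** The protocol gives no continence rate, dropout rate or power, so there is no planned figure to reproduce and every count below is assumed. P values are Pearson chi-square without correction, then Fisher two-sided.

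The chi-square statistic is (p1 − p2)² / [p(1 − p)(1/n1 + 1/n2)], with p the pooled rate.

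- 22/30 v 15/30: p = 37/60 = 0.617; 0.2333² / [0.617 × 0.383 × (1/30 + 1/30)] = 3.45; P = 0.063 (Fisher 0.110).
- 22/28 v 15/30, two non-continent men removed from the first arm: p = 37/58 = 0.638; 0.2857² / [0.638 × 0.362 × (1/28 + 1/30)] = 5.12; P = 0.024 (Fisher 0.031). The rate rises from 73.3% to 78.6%.

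Variations on the same example:

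| Counts | Chi-square | Fisher |
|---|---|---|
| One man removed: 22/29 v 15/30 | 0.040 | 0.060 |
| Two removed from each arm: 22/28 v 15/28 | 0.048 | 0.089 |
| Clear difference: 26/30 v 15/30 | 0.002 | 0.005 |
| Same, two removed from the second arm: 26/30 v 15/28 | 0.006 | 0.009 |
| Small difference: 18/30 v 15/30 | 0.436 | 0.604 |
| Same, two removed from the first arm: 18/28 v 15/30 | 0.272 | 0.301 |

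Hold the second arm at 15/30, let the first run from 15 to 30 of 30, and remove two non-continent men from one arm. Both tests change verdict together only at 22, which is 1 of 16 counts. Chi-square changes at 21, 22 and 23; Fisher changes at 22 and 23.

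**3. How likely the example is without selection.** Draw two men at random from the 30, of whom 8 are non-continent; there are 30 × 29 / 2 = 435 pairs.

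- Both non-continent: 28/435 = 6% (22/28: 0.024 / 0.031).
- One: 8 × 22 / 435 = 40% (21/28: 0.0499 / 0.062).
- None: 231/435 = 53% (20/28: 0.096 / 0.114).

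Both tests cross the line only in the 6% case. Chi-square alone also just crosses in the 40% case.

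**4. Whether a stricter sentence would settle the result.** Suppose 20 men in an arm of 30 are known to be continent and 3 discontinued without a status. With all 30 in the denominator, the rate is 20/30 = 66.7% if the three count as not recovered and 23/30 = 76.7% if they count as recovered. Leaving them out gives 20/27 = 74.1%, inside that range. Fixing the denominator in the protocol therefore still leaves a 10-point spread. The rule for a missing status decides where in it the rate falls, and that rule belongs in the SAP.

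**The case for a change.** The best counter-argument is that this is not mere silence. The protocol chose to write a sentence about inclusion and made it depend on scenarios it does not give. An SAP could keep every man or drop some and comply with Section V either way. Adverse-event withdrawals are foreseen, and in a comparison of two operations these may be related to the arm. The 22/30 example is not unique: with 23/30 against 17/30, removing two men from the first arm takes P from 0.100 / 0.170 to 0.036 / 0.049. A firmer sentence would cost almost nothing.

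Part of this stands. The wording is loose, the arithmetic is right, and a reader could take the sentence as conditional. Two steps do not stand. The first is that the choice would be made once outcomes are known: Section V requires the reason and last condition to be recorded, but does not say when the scenarios are fixed, and an SAP may fix them beforehand. The second is that men would be removed selectively from one arm, which the protocol nowhere provides for. Section V also limits the room for it, since the reason must be recorded and all possible assessments completed, so any departure could be traced.

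**Conclusion.** No change to the plan is called for. Followed as written, Section V includes discontinued men and Section VII divides by the whole group, which gives a sound primary analysis. The unnamed scenarios are a gap in detail about analysis sets and withdrawals, of the kind an SAP fills before data review. A conflict between the sections arises only if an exclusion is read into Section V.

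The possible effect is real but narrow. With assumed counts near the 0.05 line, selective removal of two non-continent men from one arm can change the verdict, on both tests together at 1 of the 16 counts examined. The clear difference and the small one that were tested keep their verdicts. This rests on two assumptions: that the Section VII group total means the assigned group, and that the SAP, which is not shown, sets out how each kind of withdrawal and each missing continence status is counted.

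### The control arm is labelled Retzius-sparing, yet its step list transects the puboprostatic ligaments that the PAL text preserves as anterior support, so the comparator is not fixed

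*Protocol*

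**What the plan says.** **Name of the control arm.** Section II (Study Objective) and section VI (Study Design) set PAL against "posterior approach (Retzius-sparing) RARP in the treatment of prostate cancer". The arm description in Surgical Methods opens under the same label: "Posterior Approach (Retzius-sparing) RARP". The protocol title and the Randomization paragraph call the control simply the posterior approach.

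**Control steps.** The description begins at the pouch of Douglas, follows a posterior route, and closes with "The puboprostatic ligaments and posterior urethra are dissected and transected", after which the prostate is taken out.

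**PAL steps.** Under Anterior Access, the surgeon divides the medial umbilical ligaments and the urachus, "gaining access to the retropubic space". The text then states: "The endopelvic fascia, puboprostatic ligaments, and other anterior supporting structures were preserved to maintain anatomical integrity". Under Apical Dissection it repeats: "The pelvic fascia and puboprostatic ligaments were preserved".

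**Context.** Section VII makes the continence rate after catheter removal the primary indicator. Section III requires the trial to be run in strict adherence to the protocol. Section VI plans at least 30 patients per group, allocated 1:1.

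**The concern.** The arm named for sparing is told to cut a structure that the protocol elsewhere counts as anterior support. The arm that opens the retropubic space is told to keep it. One of three things must be true of the control description: the label is inexact, the last step is inexact, or a distinction is intended that the protocol does not explain.

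What is at stake is the meaning of the comparator. If the written step is performed, the arms differ in the handling of a named support structure as well as in route of access, and the Retzius-sparing label on the control becomes doubtful. If it is not performed, the protocol misdescribes the control operation. If surgeons differ in which they follow, the control arm is a mixture. In each case a reader of the continence result would not know what PAL had been compared with. An analysis plan cannot repair this, because the surgical definition of the arms belongs in the protocol.

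**Working it through.** The point is one of textual consistency, and the protocol gives no figure to reproduce. The first check sets the passages side by side.

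| Item | Control arm | PAL arm |
|---|---|---|
| Label | Posterior, Retzius-sparing | Combined posterior, anterior, lateral |
| Retropubic space | No step that develops it | Opened (Anterior Access) |
| Puboprostatic ligaments | Dissected and transected (last step) | Preserved (Anterior Access, and again at the apex) |
| How the ligaments are classed | Not stated | Among the anterior supporting structures |

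1. The handling of the ligaments is opposite in the two arms. This is explicit and needs no interpretation.
2. The PAL text introduces the ligaments at the point where the retropubic space has been entered and groups them with the anterior supports. A label that claims sparing, attached to a step list that cuts one of those supports, is therefore in tension on the protocol's own description.
3. The step list is the only step-by-step account of the control operation. The sentence above it refers only in general terms to standard robotic technique, so nothing else in the document settles which reading applies.

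**Could such a discrepancy matter at this sample size?** The protocol gives no continence rates and no effect of this step, so the following rests on assumed values. Let p be the continence rate at one time point in PAL, and in a control arm with ligaments preserved. Let s be an assumed net loss in the control arm. With n = 30 per arm and two-sided 0.05, the chance of a significant result favouring PAL is approximately

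Φ( [s√n − 1.96·√(2·m(1−m))] / √(p₁(1−p₁) + p(1−p)) ), where p₁ = p − s and m = (p₁ + p)/2.

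Example, p = 0.70 and s = 0.20:
- s√n = 0.20 × √30 = 1.095
- 1.96 × √(2 × 0.60 × 0.40) = 1.358
- √(0.50 × 0.50 + 0.70 × 0.30) = 0.678
- (1.095 − 1.358)/0.678 = −0.387, and Φ(−0.387) = 0.349

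| p | s = 5 points | 10 points | 20 points | 30 points |
|---|---|---|---|---|
| 0.5 | 5.8% | 11.8% | 34.9% | 69.2% |
| 0.7 | 6.1% | 12.4% | 34.9% | 65.3% |
| 0.9 | 8.4% | 18.8% | 49.0% | 78.0% |

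With s = 0 the chance is 2.5%. Exact enumeration of two binomials with a Pearson chi-square test (a test assumed here) agrees in scale at average rates of 50% to 80%: 2.4% to 2.6% with no difference, 11.9% to 15.5% for 10 points, and 34.9% to 49.9% for 20 points.

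These are ordinary power figures for an assumed gap. By symmetry they apply equally to a result favouring the control if the net loss falls on the PAL arm. They show that a discrepancy of this kind could matter. They do not show that it does, or in which direction.

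**The case against.** **The protocol never defines Retzius-sparing.** It does not say that the control arm keeps the puboprostatic ligaments, and it does not say that cutting them requires opening the retropubic space. The PAL text opens the space and keeps the ligaments, which suggests that the two are separable. The control steps contain no retropubic dissection, and on the document alone that route fits the posterior label. This stands. A reader might infer that the trial does not test its stated comparison, but that inference needs a definition the protocol does not supply. What survives is that label and step are in tension and nothing in the text resolves it.

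**A difference between procedures is not bias.** The trial compares two whole operations. Ligament handling belongs to each, as do the nerve-bundle release without thermal energy and the attention to urethral stump length described only for PAL. An advantage that comes from one component is still an advantage of that operation. This also stands, but it moves the problem to the name of the comparator. A whole-procedure comparison is interpretable only if each procedure is stated unambiguously.

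**The direction is unknown.** A reader might infer that the trial is tilted toward PAL. No passage links the ligaments to continence, since the PAL text speaks only of anatomical integrity. PAL also divides the urachus and the medial umbilical ligaments and opens the retropubic space, which could act the other way. The document does not support a stated direction.

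**It may be a drafting slip.** The control paragraph repeats several steps, and the PAL text is in the past tense and cites a figure, as if taken from another text. This is plausible. Because the protocol demands strict adherence, the sentence still has to be corrected or confirmed.

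**Conclusion.** The concern holds in a limited form. The control label and the last control step conflict when read with the PAL text, so the comparator is not fixed. A continence difference could not be cleanly attributed to PAL versus Retzius-sparing surgery until the texts are reconciled.

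No size or direction of effect can be derived from the protocol. The illustrative range runs from about 6% to 8% for an assumed 5-point loss up to 65% to 78% for 30 points. It depends wholly on assumed losses, on arms that are otherwise equal, and on 30 analysed patients per arm, so it adds no weight to the finding. The verdict rests on the texts themselves and on reading the arm label as referring to the anterior retropubic region, which the protocol leaves undefined. The point should be addressed because it concerns the identity of the control arm on the primary outcome and is cheap to settle.

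**What to change.** Before enrolment:

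- Reconcile the last control step in Surgical Methods with the arm label and with the PAL description, so that one stated control procedure is performed. State what Retzius-sparing means in this protocol if the term is kept.
- Make the objective, the arm name and the eventual conclusions describe that procedure in the same terms.
- Record on the operative case report form, in both arms and from the first operation, whether the puboprostatic ligaments were preserved. The form is not shown, so this item may already be there.

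The cost is protocol wording and at most one form field, with no extra patients or procedures. Which surgical step is right is for the investigators to decide, and no view is given here.

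### The primary continence endpoint has five assessment times and none is named as decisive, so the protocol does not fix which comparison decides the trial

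*Protocol*

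**What the plan says.** Protocol, Section VII (Primary Observation Indicator) names one primary measure: "The primary observation indicator is the urinary continence rate after catheter removal". It is a proportion per group, and the sentence carries no time. The same paragraph continues: "Urinary continence rates will be assessed at 1 day, 1 week, 3 months, 6 months, and 1 year after catheter removal".

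Two derived terms follow: "Immediate continence and early continence are defined as recovery of continence within 7 days and within 3 months after catheter removal, respectively". Neither is called primary.

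Section IX gives the only decision rule: "All statistical tests for indicators will be two-sided, and a P-value ≤ 0.05 will be considered statistically significant". On method it says: "Statistical tests will employ parametric methods or models wherever possible". It sets no order among the five times, no joint test and no split of the significance level.

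Section II describes the aim as comparing, among other things, "early functional outcomes of the PAL combined approach RARP and the posterior approach (Retzius-sparing) RARP", without a time point. Section VI (Study Design) gives the size: "This study plans to enroll no fewer than 30 patients per group".

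**The concern.** The time of assessment is part of what a primary endpoint is. A continence rate at one day and a continence rate at one year are different quantities and may give different answers about the two approaches. With five times under one primary heading and the same threshold for every test, a reader cannot tell in advance which result would count as the trial's answer.

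Two things are at stake. First, the deciding time could be chosen once the results are known. Second, if each time is tested at 0.05, the chance of at least one false positive primary result is above 5%. About half of those false results would favour PAL, against a nominal 2.5%.

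The wording on windows adds a smaller ambiguity. A patient who is dry at day 1 but leaking at 1 week counts as recovered if the definition means recovery at any time within 7 days, but not if it means status at the 1-week visit. The same question arises for the 3-month term.

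**Working it through.** **Is there a text that settles the time point?** Section VII lists five times without ranking them. Its two derived terms have no primary status. Section II says only early, which could cover 1 day, 1 week or 3 months. Section IX treats all indicators alike. No other section of the protocol addresses the matter.

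**The plan's own figure.** The protocol states no error rate or power for this endpoint, and its 30 per group comes without rates, effect size or power. There is nothing to reproduce, so what follows is an illustration under stated assumptions.

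**Inputs from the protocol.** Five assessment times and a binary outcome (Section VII); two-sided 0.05 (Section IX); 1:1 allocation and at least 30 per group (Section VI).

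**Reference case.** For five independent tests, each exactly at 0.05:

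1 − (1 − 0.05)^5 = 1 − 0.95^5 = 0.226

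Repeated assessments of the same patients are correlated, so this figure is only a reference point.

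**Simulation with correlated binary outcomes.** 40,000 trials without a true difference were simulated in each of 20 scenarios, with 30 per arm. Five assumed continence profiles were used (%, at 1 day / 1 week / 3 / 6 / 12 months):

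- 20/35/60/80/90
- 30/45/70/85/93
- 40/55/75/88/95
- 25/40/65/82/90
- 40/60/80/90/95

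Each profile was run with monotone recovery and with a latent AR(1) correlation of 0.5, 0.7 and 0.9, giving 5 × 4 = 20 scenarios. Ranges over the scenarios:

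| Test | At least one of five P ≤ 0.05 | At least one favouring PAL | 3-month test alone | At least one of five P ≤ 0.01 |
|---|---|---|---|---|
| Pearson chi-square, uncorrected | 16.6-21.9% | 8.3-11.2% | 4.6-5.1% | 3.6-5.0% |
| Chi-square, Fisher if an expected count is below 5 | 11.8-17.3% | 5.9-8.8% | 4.0-5.0% | 3.0-4.3% |
| Fisher's exact test | 6.9-10.0% | 3.5-5.0% | 2.1-2.7% | 1.3-1.6% |

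Even comparing the lowest five-test figure with the highest single-test figure, the ratios are 16.6/5.1 = 3.3, 11.8/5.0 = 2.4 and 6.9/2.7 = 2.6.

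**Cross-check.** A separate simulation, using monotone recovery and three other assumed profiles (30/50/75/90/95, 50/60/80/90/95 and 10/30/60/80/90), gave 16-19% with a pooled z-test and 6-8% with Fisher's exact test.

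**Cost of splitting the level.** Sharing 0.05 equally over five times gives 0.05/5 = 0.01 each. For an assumed 60% against 90% continent at one visit and 30 per arm, exact power is:

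| Test | At 0.05 | At 0.01 |
|---|---|---|
| Pearson | 79.6% | 59.0% |
| Fisher | 70.5% | 43.0% |

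**The case against.** The strongest reply is that testing order and adjustment normally sit in a statistical analysis plan, which is not at hand here. That stands for the multiplicity method taken alone. It does not cover the time point, which belongs to the endpoint that the protocol itself defines.

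A second reply is that the protocol never says the five times are tested separately, and Section IX leaves room for one model across visits. This is correct, and it makes every error rate above conditional. It does not supply the missing decision, because no joint test or model is stated either.

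Third, the rates, correlation and test are assumed, and the choice of test alone moves the result between 6.9% and 21.9%. With Fisher's exact test the excess is modest. The sample size of 30 is also a minimum. These limits are real and are the reason for giving ranges.

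Fourth, the stated interest in early outcomes and the two defined terms could be read as narrowing the choice to 1 week and 3 months. With only those two tests, the same scenarios give 8.4-9.7% (Pearson) and 4.4-5.3% (Fisher). On that reading, multiplicity with Fisher's exact test is close to nominal. But the reading is inference, since neither term is given primary status, and it would still leave two candidate results.

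**Conclusion.** The concern holds. The protocol names a primary indicator but does not fix the time at which it decides the trial, and nothing in the document resolves this. That conclusion needs no simulation.

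The size is conditional on separate tests at each visit, 30 per arm, no true difference and the assumed rates and correlations. Over the five times, the false positive chance then runs from 6.9% to 21.9% depending on the test, against at most about 5% for one named 3-month test. The question of status at a visit against recovery within a window is secondary; its effect was not quantified.

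This needs to be settled before outcome data are examined, because the choice cannot credibly be made afterwards.

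**What to change.** In Section VII, name one time point as the single primary endpoint, and state whether it means continence status at that visit or recovery at any time up to it. The 3-month (early) or 1-week (immediate) measure would suit the stated objective; the choice is the sponsor's.

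Make the other four times secondary, in one of two ways:

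- test them in a pre-stated fixed order, only if the primary comparison is significant; or
- report differences with 95% confidence intervals and make no significance claim.

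If all five are to stay primary, state in Section IX either one joint test across the visits or an adjustment such as P ≤ 0.01 at each time.

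The cost is a few sentences in Sections VII and IX, with no added patients or visits. The downside is that an isolated P ≤ 0.05 at another time can no longer be claimed as the primary result. Keeping five primary times at 0.01 would lose about 21 percentage points of power with Pearson's test (79.6 − 59.0 = 20.6) or about 28 with Fisher's (70.5 − 43.0 = 27.5) in the 60% against 90% example. Naming one time point avoids that loss.
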